## 5.2 Study Periods

### 5.2.1 Screening Period

Patients will provide written informed consent to participate in the study before completing any protocol-specified procedures or evaluations not considered to be part of the patient's standard of care. Procedures that were performed for standard of care prior to signing informed consent may be used for screening purposes (eg, full physical examination) as long as the procedures were completed within the window of that assessment during the Screening period (Section 1.2). After signing the informed consent form (ICF), patients will be evaluated for all eligibility criteria during the Screening period before administration of study drug(s). Rescreening after screen failure will be allowed after consultation with the Medical Monitor. The Screening window is 28 days. Baseline scan(s) available up to 14 days prior to signing the ICF are acceptable.

### 5.2.2 Assigning Patient Numbers

Each patient will be assigned a unique patient number after signing the ICF. Patient numbers will be used on all patients' study information. Patient numbers will not be reassigned.

### 5.2.3 Treatment Period

Patients will remain on treatment until meeting one of the criteria for discontinuation of treatment in Section 5.2.3.1. In the event of a patient's withdrawal, the Investigator will promptly notify the Sponsor and make every effort to complete the End of Treatment (EOT) procedures specified in the Schedule of Events (Section 1.2). Patients will continue to be followed for safety and survival as per Sections 5.2.6 and 5.2.7, respectively.

If scheduled visits or assessments coincide with a weekend or holiday, schedule at the next feasible date. Please contact the Medical Monitor to discuss any concerns about study visits or assessments that may fall out of the protocol-specified window because of unforeseen delays or other patient-specific circumstances. The allowable windows for PK and immunogenicity sampling, and vital signs on PK collection days is provided in [Table 6](#). All out-of-window visits and procedures will incur a protocol deviation.

Patients will remain on study until meeting one of the criteria for discontinuation of study in Section 5.2.3.3. Patients may choose to discontinue the trial at any time, for any reason, and without prejudice to further treatment.

Patients in Phase 1b (dose escalation) or Phase 2 Cohorts A, B, C1, D1, and/or E1 who achieve an optimal response (CR or PR per RECIST 1.1) after at least 1 tumor assessment, as determined by the Investigator and in consultation with the Medical Monitor, may transition to a q28d schedule of single-agent NKTR-255 as maintenance at the same dose as the patient's originally assigned dose.

Patients receiving monotherapy NKTR-255 who do not achieve optimal response will have the option to receive cetuximab add-on.

See Section [5.2.5](#) for information about treatment beyond progression.

### **5.2.3.1 Criteria for Discontinuation from Treatment**

Study treatment may be discontinued for any of the following reasons:

- Any clinical AE, laboratory abnormality, or intercurrent illness that would, in the judgment of the Investigator, affect assessments of clinical status to a significant degree
- Toxicity that, despite maximum medical management, in the judgment of the Investigator, compromises the ability to continue study-specific procedures or is considered to not be in the patient's best interest
- Disease progression (based on Investigator assessment of baseline and post-baseline scans as per RECIST 1.1). In some circumstances patients may be treated beyond disease progression. Details are provided in Section [5.2.5](#).
- Patient request to discontinue treatment for any reason
- Patient noncompliance
- Initiation of systemic antineoplastic therapy other than treatments per protocol in the absence of progression
- Discontinuation of the study treatment at the request of Nektar, a regulatory agency or an institutional review board (IRB) or independent ethics committee (IEC)
- Pregnancy during treatment
- Death
- Investigator's decision, in consultation with the Medical Monitor

If a patient discontinues NKTR-255, the patient may continue on cetuximab alone, at the discretion of the Investigator, until disease progression or initiation of systemic anti-tumor therapy (whichever is earlier).

If a patient discontinues study drug(s), every attempt should be made to continue tumor assessment at every 9 weeks until disease progression or initiation of systemic anti-tumor therapy. The patient will be asked to attend the 60-day post-treatment follow-up assessment visit when discontinuing from the study treatment.

### **5.2.3.2 End of Treatment Visit**

Patients will remain on study until meeting one of the criteria for discontinuation of study in Section [5.2.3.3](#). Patients who are discontinued will complete the EOT visit and all safety follow-up procedures as per the Schedule of Events (Section [1.2](#)). The EOT visit should occur

within 7 days after study treatment is discontinued, and before a new antineoplastic regimen has been initiated.

### **5.2.3.3 Criteria for Discontinuation from Study**

Patients who discontinue study treatment due to any of the treatment discontinuation criteria in Section 5.2.3.1 will continue to be followed for survival per Section 5.2.7.

In the event of an unscheduled study termination by the Sponsor, patients who are on-treatment at the time of the end of the study will be followed for safety for 60 days post EOT as per Section 5.2.6.

Criteria for study discontinuation may include:

- Withdrawal of consent from study
- Loss to follow-up
- Death
- Discontinuation of the study at the request of Nektar, a regulatory agency or an IRB/IEC
- Principal Investigator's decision
- Medical Monitor's assessment due to lack of adherence to protocol

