### **5.2.7 Survival Follow-up**

Following discontinuation of study treatment, patients will be contacted approximately every 3 months  $\pm 14$  days after the EOT by clinic visit or telephone, or other alternate methods such as email, contact with family, or public records (if allowed per local regulations), to obtain the information about alternative anti-cancer therapy and assess survival information until the patient meets the criteria for study discontinuation in Section [5.2.3.3](#).

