**Table 3: PFS Censoring Rules**

Situation	Date of Disease Progression or Censoring	Outcome
No post-baseline tumor assessments and no death	first dose date of Cetuximab	Censored
No progression and no death, and no new anti-cancer therapy started	Date of last assessment showing no evidence of disease progression	Censored
New anti-cancer therapy started without progression before	Date of last assessment before the start of anti-cancer therapy showing no evidence of disease progression	Censored
Disease progression reported on one or multiple response assessments without new anti-cancer therapy before	Date of earliest evidence of PD	Progressed
Death without PD or new anti-cancer therapy before	Date of death	Death
Two or more consecutive missing tumor assessments, and no progression before the missing assessment	Date of the last assessment prior to the missing assessment showing no evidence of disease progression	Censored

**Overall Survival (OS):** OS is defined as the time from the first dose date of Cetuximab to death from any cause. Patients will be followed until their date of death, loss to follow-up, or withdrawal of consent for further follow-up for survival, regardless of the start of anti-cancer therapy. Patients who are lost to follow-up will be censored at their last date known to be alive. Patients who do not have date of death at data cut-off date will be censored at their last date known to be alive. Patients who do not have any follow-up since first dose date of Cetuximab will be censored on the first dose date of Cetuximab.

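### Removal from study by the investigator or Medical Monitor ends survival follow-up under the protocol but not under the SAP, so OS can be censored for reasons linked to prognosis.

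*Protocol*

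**What the plan says.** Protocol 5.2.3.3 gives reasons for leaving the study. Besides consent withdrawal, loss to follow-up, death and termination by the sponsor, a regulator or an ethics body, it lists "Principal Investigator's decision" and the Medical Monitor's "assessment due to lack of adherence to protocol". The list is introduced as what the criteria may include.

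Protocol 5.2.7 has sites contact patients about every 3 months after end of treatment and "assess survival information until the patient meets the criteria for study discontinuation" in 5.2.3.3. Contact may be by clinic visit, telephone, email, family or public records.

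Protocol 5.2.3.1 gives reasons for stopping treatment, including "Patient noncompliance" and an investigator's decision taken with the Medical Monitor. According to the opening of 5.2.3.3, patients who stop treatment for any of those reasons "will continue to be followed for survival per Section 5.2.7".

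The OS definition in SAP 6.6.1 states: "Patients will be followed until their date of death, loss to follow-up, or withdrawal of consent for further follow-up for survival". It censors any patient without a death date at the last date known alive. SAP 6.6 accepts the study-discontinuation date as a source for that date unless the reason was loss to follow-up. SAP section 12, which lists changes from the protocol, does not mention OS follow-up.

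**The concern.** Two documents that should describe the same follow-up end it at different points. Under the protocol, a discretionary decision by the investigator or Medical Monitor closes survival follow-up. The SAP's OS definition names no such reason.

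What is at stake is the censoring assumption. Kaplan-Meier treats a censored patient as having the same future risk as those still followed. In a salvage population, patients who miss visits or are withdrawn by the investigator may well be those who are deteriorating. If so, deaths soon after removal are lost and OS looks better than it is. A larger sample would not correct this. Nor is adherence needed to learn whether a patient is alive, since 5.2.7 already permits telephone and public-record contact.

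The boundary between the two protocol sections is also unclear. Noncompliance or an investigator's decision leaves a patient in survival follow-up if recorded as a reason to stop treatment, and takes the patient out if recorded as a reason to leave the study. Two sites could code the same patient differently.

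**Working it through.** **Step 1: the texts side by side.**

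| Reason | Protocol 5.2.3.3 with 5.2.7 | SAP 6.6.1 (OS) |
|---|---|---|
| Death, loss to follow-up | ends survival follow-up | ends it |
| Withdrawal of consent | ends it (consent from study) | ends it (consent for survival follow-up) |
| Investigator's decision | ends it | not named |
| Medical Monitor, non-adherence | ends it | not named |
| Sponsor, regulator or ethics-body termination | ends it | not named in that sentence |

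**Step 2: where the patient is censored.** Once contact stops, the last date known alive will usually be the removal date or close to it (SAP 6.6 and 6.6.1).

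**Step 3: how wide the route is.** Protocol 11.1 says a deviation may lead to withdrawal from the study. Section 5.2.3 and Table 1 footnote a count every out-of-window visit or procedure as a deviation. A patient who misses visits because of decline could therefore be removed under the protocol's own terms.

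**Step 4: size, by illustration.** The documents give no expected OS, removal rate or OS event count, so there is no planned figure to reproduce. All inputs here are assumptions except n = 30, the approximate Phase 1b size in Protocol 9.2: exponential survival with median m, so S(12) = 0.5^(12/m); administrative censoring at 24 months; 40,000 simulated patients per setting; removed patients censored about 1 month before death.

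| m (months) | True S(12) | 3% removed | 10% removed | 20% removed |
|---|---|---|---|---|
| 6 | 25.0% | 25.8% | 28.6% | 31.9% |
| 9 | 39.7% | 41.0% | 42.9% | 47.4% |
| 12 | 50.0% | 50.8% | 53.6% | 57.0% |

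The upward shift is about 1 point at 3% removed, 3 to 4 points at 10% and 7 to 8 points at 20%. True medians of 6, 9 and 12 months are estimated as 6.5, 9.8 and 13.4 with 10% removed, and 7.3, 11.1 and 14.8 with 20% removed. When removal times are independent of death, 12-month OS stays within about 0.3 points of the truth.

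**Step 5: a hand check.** Take 30 patients with 12 alive at 12 months: 12/30 = 40%. Suppose k patients who would die within the year are censored near the start. The estimate is then 12/(30 − k): 12/29 = 41.4%, 12/27 = 44.4%, 12/25 = 48.0% for k = 1, 3, 5. These are upper-end values, because removal comes at the start and every removed patient is an early death.

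**Step 6: against random error.** The half-width is 1.96 × √(p(1 − p)/30), by simple binomial approximation. It is 15.5 points at p = 0.25, 17.5 at p = 0.40 and 17.9 at p = 0.50.

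**The case against.** A reader might infer three stronger things, and the documents support none of them.

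- **That OS is in fact biased.** The documents report no removals, no rate and no pattern of reasons, and the list in 5.2.3.3 is permissive. The link to prognosis is a reasonable inference, not a documented fact. If removal is unrelated to prognosis, the estimate is essentially unaffected (step 4).
- **That 5.2.3.3 contradicts itself.** Noncompliance as a treatment reason sits in 5.2.3.1. Stopping treatment and leaving the study are different levels, and a patient can do the first without the second. What remains is an unclear boundary between two sections.
- **That the SAP sentence is an exhaustive list which the protocol breaches.** It does not name sponsor termination either, and the SAP separately censors anyone without a death date. This softens the conflict but does not remove it: a protocol route that ends OS follow-up early is neither reflected in the SAP's definition nor listed among its changes.

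Two further points stand. SAP 7.1 tabulates reasons for study discontinuation and lists disposition data, so such removals would be visible, although no OS sensitivity analysis follows from them in the text available. And OS is a secondary endpoint summarized descriptively, in about 30 patients reported separately for HNSCC and CRC. The Phase 1b primary endpoints (DLTs and treatment-emergent AEs) do not depend on survival contact.

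**Conclusion.** The point holds as a mismatch between the protocol and the SAP on when survival follow-up ends, with a possible and avoidable source of informative censoring. That part rests on the text alone.

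The bias is conditional. It requires that patients are actually removed for these reasons and that removal tends to precede death. Under the assumptions shown, with 10% to 20% removed, 12-month OS is overstated by about 3 to 8 points, which is well inside the random error at n = 30. With about 3% removed (roughly one patient in 30) the shift is about 1 point. Importance is modest. The change is worth making because it is cheap and because this error, unlike sampling error, can be prevented.

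**What to change.** **Protocol.** Amend 5.2.7 so that survival follow-up ends only at death, loss to follow-up, withdrawal of consent for survival follow-up, or study end or termination. State in 5.2.3.3 and in 11.1 that removal by investigator or Medical Monitor decision, or for a protocol deviation, does not by itself end survival follow-up. The two entries in 5.2.3.3 need not be moved, since 5.2.3.1 already has near-equivalents. No treatment rule changes, and patients who withdraw consent to survival follow-up are still left alone.

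**SAP and report.** The SAP says only Phase 1b patients were enrolled, so a protocol change alone cannot help anyone already removed. For such patients, obtain vital status where permitted, report their number, reasons and censoring dates, and add an OS sensitivity analysis that counts them as deaths at or soon after removal. That serves as a pessimistic bound. Name study end or termination in the OS definition so that the two documents agree.

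**Cost.** A few extra 3-monthly contacts of a kind already planned, short wording changes, and one extra descriptive analysis.

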### **5.2.3.4 Replacement of Patients**

In the dose escalation portion, patients who do not complete the DLT observation period for reasons other than a DLT may be replaced to provide a sufficient number of patients for adequate evaluation of each dose escalation level.

Patients will not be replaced during the dose expansion portion of the study.

### **5.2.4 Maintenance Period**

Patients in Phase 1b (dose escalation) **CCI** who achieve optimal response (PR or CR per RECIST 1.1) after at least 1 tumor assessment, as determined by the Investigator and in consultation with the Medical Monitor, will be given the option to continue treatment with NKTR-255 as single agent for maintenance q28d at the same dose as the patient's originally assigned dose.

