The first patient (a sentinel patient) of each escalating NKTR-255 dose level will be monitored for safety and tolerability for 7 days after the first dose of NKTR-255 before additional patients are dosed at the same dose level.

A composite of clinical information will be used to select the RP2D based on safety and tolerability, PK, PD, and optimal biological response. Additional patients may be enrolled to refine the RP2D, and a minimum of 6 patients will be required to define the RP2D.

The dose-limiting toxicity (DLT) window is 21 days after the first dose of NKTR-255.

Patients who achieve optimal response (partial response [PR] or complete response [CR] per RECIST 1.1) after at least 1 tumor assessment, as determined by the Investigator and in consultation with the Medical Monitor, will be given the option to continue treatment with NKTR-255 as single agent for maintenance every 28 days (q28d) at the same dose as the patient's originally assigned dose.

CCI

- Intermediate doses may be evaluated.
- No intra-patient dose escalation will be allowed.
- Enrollment into a new dose level with an escalating dose of NKTR-255 cannot begin until the DLT window has closed for at least 3 patients in the prior dose level.
- The SRC will assess safety before opening dose escalation to the next level.
- The Sponsor's decision to declare the RP2D of NKTR-255 can occur at any given dose level prior to reaching the MTD based on safety, PK, CCI effects.
- Data from a minimum of 6 evaluable patients are required to define the RP2D.
- Dose reduction of NKTR-255 is not allowed during dose escalation within the DLT window. Outside of the DLT window in the dose escalation phase, and during dose expansion, dose levels of NKTR-255 may be reduced depending on the severity, duration, and frequency of toxicities observed at the previous dose level tested (the dose level may be de-escalated in order to characterize RP2D for a specific dose level).
- The cetuximab dose may be reduced or adjusted based on review of available safety and tolerability data. Dose adjustment or discontinuation for cetuximab may be required

based on emerging toxicities, and should follow the guidelines specified in this protocol and in the current local prescribing information for cetuximab.

CCI

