**CCI**

CRC = colorectal cancer; **CCI**

HNSCC = head and neck

squamous cell carcinoma; Ph = Phase; RP2D = recommended Phase 2 dose

Note: No intra-patient dose escalation will be conducted in any dose level.

Note: The dose-limiting toxicity (DLT) window for NKTR-255 in combination with cetuximab is 21 days following the initial dose of NKTR-255.

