**Table 1: Schedule of Visits and Assessments – Phase 1b (CRC and HNSCC; NKTR-255 Dose Escalation) (Contd)**

Event a	Screening Period	Treatment Period																		Post-treatment Period									
		Run-in (1 week) Day			Cycle 1 (21-day cycle) Day						Cycle 2 (21-day cycle) Day						Cycle 3 (21-day cycle) Day			Cycle 4+ (21-day cycles) Day									
		≤ 28d prior to Day 1 of Run-in Period			-7	-6	-4	1	2	3	4	5	8	10	15	1	2	3	4	8	10	15	1	4	8	15	EOT b	60-day Follow-up c	Survival Follow-up c
Windows (days)		+1			+1										+1							+1			+1		+7	±14	Every 3 months ±14 days
Study Drug Administration																													
NKTR-255 administration u						X									X							X			X				
Cetuximab administration v			X			X				X	X	X				X		X	X	X	X	X	X	X					
Concomitant medications review	Continuous from time of ICF until 60 days after last study treatment dose																												
Efficacy Assessments																													
Tumor measurements and RECIST 1.1 and irRECIST response assessments w	Tumor assessments at Screening and every 9 weeks from C1D1 + 7 days until patients meet one of the criteria for discontinuation of treatment in Section 5.2.3.1.																												
Subsequent therapy/survival/secondary malignancy information																							X	X	X				

AE = adverse event;  $\beta$ -HCG = beta subunit of human chorionic gonadotropin; CK = creatine kinase; CnDn = Cycle n Day n; CRC = colorectal cancer; d = day; ECG = electrocardiogram; EBV = Epstein-Barr virus; ECOG = Eastern Cooperative Oncology Group; EOI = end of infusion; EOT = end of treatment; HBV = hepatitis B virus; HCV = hepatitis C virus; HIV = human immunodeficiency virus; HNSCC = head and neck squamous cell carcinoma; HPV = human papillomavirus; ICF = informed consent form; irRECIST = immune-related RECIST 1.1; IV = intravenous(ly); LVEF = left ventricular ejection fraction; MRI = magnetic resonance imaging; MUGA = multigated acquisition; PaO2 = oxygen saturation; CCI [REDACTED] PK = pharmacokinetic(s); PT = prothrombin time; PTT = partial thromboplastin time; q21d = every 21 days; q3 = every 3; RECIST = Response Evaluation Criteria In Solid Tumors; T3 = triiodothyronine; T4 = thyroxine; TSH = thyroid-stimulating hormone; WCBP = women of childbearing potential

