Eligible patients will receive cetuximab 400  $\text{mg}/\text{m}^2$  IV as a loading dose during the study run-in period (Day -7). Thereafter, cetuximab 250  $\text{mg}/\text{m}^2$  IV will be administered weekly and NKTR-255 will be administered q21d. The DLT window is 21 days after the first dose of NKTR-255. Patients who achieve optimal response (partial response [PR] or complete response [CR] as determined by RECIST 1.1) after at least 1 tumor assessment, as determined by the Investigator and in consultation with the Medical Monitor, will be given the option to continue treatment with NKTR-255 as single agent for maintenance every 28 days (q28d) at the same dose as the patient's originally assigned dose.

CCI [REDACTED]

The logo consists of the letters 'CCI' in a large, bold, red sans-serif font. The letters are slightly overlapping, with 'C' on the left, 'C' in the middle, and 'I' on the right. The background is a solid black rectangle.

- Intermediate doses may be evaluated.
- No intra-patient dose escalation will be allowed.
- Enrollment into a new dose level with an escalating dose of NKTR-255 cannot begin until the DLT window has closed for at least 3 patients in the prior dose level. The DLT window is 21 days after the first dose of NKTR-255.
- The SRC will assess safety before opening dose escalation to the next level.
- The Sponsor's decision to declare the RP2D of NKTR-255 can occur at any given dose level based on safety, PK or CCI ██████ effects without reaching the MTD.
- Data from a minimum of 6 evaluable patients are required to define the RP2D.
- Dose reduction of NKTR-255 is not allowed during dose escalation within the DLT window. Outside of the DLT window in the dose escalation phase, and during dose expansion, dose levels of NKTR-255 may be reduced depending on the severity, duration, and frequency of toxicities observed at the previous dose level tested (the dose level may be de-escalated in order to characterize RP2D for a specific dose).
- The cetuximab dose may be reduced or adjusted based on review of available safety and tolerability data. Dose adjustment or discontinuation for cetuximab may be required based on emerging toxicities, and should follow the guidelines specified in this protocol and in the current local prescribing information for cetuximab.

CCI

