### **5.3 Administration of Study Drug(s)**

#### **5.3.1 NKTR-255 Dosing**

Dose administration is shown in [Figure 2](#) and [Figure 3](#). NKTR-255 will be administered as a 30-minute infusion, q21d as monotherapy and in combination with cetuximab, and q28d as single-agent maintenance at the same dose as the patient's originally assigned dose. For applicable dose levels or cohorts (Phase 1b **CCI** [REDACTED]), cetuximab will be given weekly. **CCI** [REDACTED]  
[REDACTED]

The dose does not need to be recalculated for weight changes that are < 10% from baseline (Day -7).

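### Maintenance NKTR-255 is set at the originally assigned dose, and no readable text carries over a patient's earlier dose reduction

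*Protocol*

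**What the plan says.** **Maintenance dose.** Five readable places in the protocol give the same rule: the synopsis ("for maintenance every 28 days (q28d) at the same dose as the patient's originally assigned dose"), Section 5.1.1, Section 5.2.3 ("may transition to a q28d schedule of single-agent NKTR-255 as maintenance at the same dose as the patient's originally assigned dose"), Section 5.2.4 ("NKTR-255 as single agent for maintenance q28d at the same dose as the patient's originally assigned dose") and Section 5.3.1 ("q28d as single-agent maintenance at the same dose as the patient's originally assigned dose"). SAP Section 5.0 repeats it. The option opens for a PR or CR after at least one tumour assessment.

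**Reductions.** Section 5.1.1 states: "Outside of the DLT window in the dose escalation phase, and during dose expansion, dose levels of NKTR-255 may be reduced". That sentence goes on largely in terms of dose levels, so the clear patient-level rule is Section 5.3.1.5. There, after a Grade 3 toxicity has recovered, dosing may restart one dose level lower. A Grade 2 toxicity that persists past the end of the cycle may also lead to a delay or reduction. Adjustments need the Medical Monitor's approval and are barred within the DLT window.

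**Escalation ban.** Section 5.1.1: "No intra-patient dose escalation will be allowed". The note to Figure 1: "No intra-patient dose escalation will be conducted in any dose level". Neither says whether returning to the assigned dose after a reduction counts as escalation.

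**Timing of scans.** Table 1: "Tumor assessments at Screening and every 9 weeks from C1D1 + 7 days".

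**The concern.** The originally assigned dose and the dose a patient is currently receiving differ only when the dose has been changed. For everyone else the wording is harmless. For a responder reduced for toxicity, it names the dose that was found to be too much for that patient.

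What is at stake is patient safety and clear dosing instructions. A site with such a patient has a written maintenance dose that is higher than the current one, and a general statement that doses are not escalated within a patient. Nothing readable says which governs. The affected patients are those reduced for Grade 3 or persistent Grade 2 toxicity who stayed on treatment and then responded. No endpoint analysis turns on this.

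**Working it through.** The plan gives no figure on this point to reproduce. The check is a comparison of texts, followed by short arithmetic on timing and dose intensity.

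**1. Is a carry-over stated?** The synopsis and Sections 5.1.1, 5.2.3, 5.2.4 and 5.3.1 all name the originally assigned dose, without exception. Section 5.3.1.5 permits reductions but does not mention maintenance. Section 5.3.1.6 allows a restart at the same dose level after an adverse event resolves; it covers restarting after a delay and does not address a reduction already made. No readable text carries a reduction forward.

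**2. Can a reduction come before maintenance?** Take C1D1 as Day 1, 21-day cycles, and a DLT window that closes with Cycle 1 (Section 5.9 bases the MTD on DLTs in Cycle 1).

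- C2D1 = 1 + 21 = Day 22; C3D1 = Day 43; C4D1 = Day 64.
- First scheduled scan = 1 + 63 = Day 64, or up to Day 71 with the 7-day window.
- Infusions after the DLT window and before that scan: two (Days 22 and 43), or three if the scan follows C4D1.

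This count assumes undelayed dosing and a response at the first scheduled scan. Dose delays or an unscheduled scan (allowed by Section 8.2) would lower it, and a later response would raise it. The sequence is possible; how often it happens is not known.

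**3. What happens to the dose?** Let r = reduced dose / assigned dose, with r < 1.

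- Per-infusion dose on entering maintenance, relative to the reduced dose: 1/r.
- Schedule effect of moving from q21d to q28d: 21/28 = 0.75.
- NKTR-255 intensity relative to the reduced q21d regimen: (1/28)/(r/21) = 0.75/r. This is a rise only if r < 0.75.
- NKTR-255 intensity relative to the originally assigned q21d regimen: 0.75.

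The dose levels above the 1.5 µg/kg start are not readable, so r is unknown. The values below are assumptions for illustration:

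| r (assumed) | Per-infusion factor 1/r | Intensity vs reduced regimen 0.75/r |
|---|---|---|
| 0.75 | 1.33 | 1.00 |
| 2/3 | 1.50 | 1.13 |
| 0.50 | 2.00 | 1.50 |

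The last row corresponds to adjacent levels a full doubling apart. The 100% figure in Section 5.8 caps upward steps between dose levels and does not set the size of a reduction.

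**4. Does this reach the DLT or MTD estimates?** No. Within-patient adjustments are barred inside the DLT window, and the MTD is estimated from Cycle 1. Maintenance comes later.

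**The case against.** **The ban may not apply.** It sits among the rules for opening new dose levels, and the figure note ties it to dose levels. Read as forbidding any dose above the patient's assignment, it agrees fully with the maintenance rule. It also names no dose. This stands: a reader might infer that the protocol contradicts itself, but the ban is undefined and the documents do not establish a contradiction. The literal maintenance rule still returns the patient to the dose that was lowered, whichever way the ban is read.

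**Redacted text may resolve it.** Sections 5.3.1.1 to 5.3.1.3 and 5.11 cannot be read, and blacked-out text follows the maintenance sentence in the synopsis and Section 5.1.1. A carry-over rule could be there. This also stands, so the point is confined to the readable text.

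**Safeguards exist.** Dose adjustments need Medical Monitor approval, and going back up is arguably an adjustment. Maintenance is optional. Sections 5.3.1.5 and 5.7 take most of the severest toxicities off treatment. A reader might infer that patients are re-escalated automatically; the text does not support that. One qualification: in Section 5.2.4 the consultation with the Medical Monitor is attached to judging the response, not to choosing the dose.

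**Rechallenge is defensible.** Maintenance drops cetuximab, whose adverse effects Section 5.12 says may be enhanced by the combination, and lengthens the interval. Intensity is 0.75 of the original regimen, so it would be wrong to infer that the patient returns to the exposure at which the toxicity arose. Only the per-infusion dose returns. If rechallenge is intended, the protocol should say so; at present it follows from wording that does not mention reductions.

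**Conclusion.** The point holds in limited form and is **minor**. On the readable text, a Phase 1b responder reduced under Section 5.3.1.5 would enter maintenance at the higher, originally assigned per-infusion dose. This fits poorly with the ban on intra-patient escalation if the ban covers re-escalation after a reduction, which is left undefined.

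The per-infusion rise is 1/r. Dose intensity rises against the reduced regimen only when r is below 0.75. No number of patients can be given, and it may be zero. SAP Section 2.0 states that only Phase 1b patients were enrolled, so no Phase 2 responders are involved. Nothing here touches the DLT or MTD estimates.

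The conclusion rests on two assumptions: that no redacted section already carries the reduction over, and that sites would read the maintenance sentence literally.

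**What to change.** In the protocol synopsis and Sections 5.1.1, 5.2.3, 5.2.4 and 5.3.1, replace the dose phrase with: *at the originally assigned dose or, if reduced under Section 5.3.1.5, at the reduced dose being received at transition*. If a redacted section already says this, a cross-reference from Section 5.2.4 is enough. SAP Section 5.0 can be aligned for consistency.

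An absolute bar on any later increase is not needed: it would go beyond carrying the reduction over and would remove the Medical Monitor's discretion.

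The cost is one phrase in five places, with no added patients, procedures or tables. The downside is lower maintenance exposure in the few reduced responders: 0.75r of the originally assigned dose intensity, against 0.75 under the present wording.
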